3.2.10.4. Sample Size Determination

Our sample size calculation is based on the primary aim. We hypothesize that polyp resection with clip closure of the mucosal defect will reduce the incidence of delayed bleeding complications. Prior studies have reported an overall bleeding incidence between 2 and 24% (table 1). We consider an absolute difference of 5% in delayed bleeding incidence (e.g. 8% and 3%) as clinically important. Assuming a two-sided alpha of 0.05 and a power of 80%, the study will need to include a total of 730 subjects (365 subjects into each group) to show such difference as significant. We assume that for approximately 20% of patients clip

closure will not be considered possible. Therefore approximately 920 patients will need to be included. However, approximately 10% of potential study polyps of referred patients will not meet inclusion criteria (screen failures). We estimate therefore that we need to enroll (=consent) a total of 1,020 patients for 920 patients to undergo the study intervention.

Because the primary outcome measure (delayed bleeding) will be assessed after 30 days of the colonoscopy we do not expect any dropouts.

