3.2.5. Allocation to treatment (Randomization process)

Randomized will occur at the time of colonoscopy when a polyp has been identified as a study polyp using computer generated randomization. Patients will be randomized following a 2 x 2 factorial design to: (i) Endocut vs. low power coagulation after inspection of the polyp and decision to resect the polyp, and (i) clipping vs. no clipping of the mucosal defect after resection.

Patients will hence be randomized to one of four groups:

- A) Endocut and clipping,
- B) Endocut and no clipping,
- C) Low power coagulation and clipping, and
- D) Low power coagulation and no clipping.

Should a patient have more than one study polyp, all polyps will be resected in the same way (per patient randomization). The primary comparison will be between clip and no clip application. The comparison between cautery currents is secondary and exploratory.

Breaking the blind: The study is not blinded.

Treatment adherence/study compliance: The primary intervention (one-time clip placement) does not require adherence to the intervention. Participants will therefore not be excluded because of non-compliance.

The major outcome of interest will be assessed after 30 days following the intervention by a phone call. We expect that such short interval will allow an almost complete follow-up.

Secondary outcomes of interests include polyp recurrence during longer-term follow-up. We will collect data on all follow-up procedures that are performed as per standard of care (not as a study intervention).

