3.2.9.2. Study endpoints

Endpoints of primary analysis (Comparison between clip group versus no-clip group within 30 days of follow-up):

Primary endpoint:

- *Delayed bleeding complications:*

Delayed bleeding is a serious adverse event that is defined as a patient who left the endoscopy unit and subsequently had to return to any health care facility for evaluation of rectal bleeding AND who required either hospitalization, transfusion, a repeat colonoscopy or sigmoidoscopy for examination of the polypectomy site or control of bleeding, or surgery within 30 days after completion of the colonoscopy.

Secondary endpoint:

- *Complications overall:* Overall complications will be defined as an aggregate of all complications that occur at the time of the procedure (immediate complications) or during 30 days of follow-up. They include bleeding complications as defined above, perforation, postpolypectomy syndrome, and clinical events that require an ED visit, admission to the hospital, or additional testing or intervention.

Explorative:

- *Immediate and delayed complications:* Immediate complications are considered all complications at the time of polyp resection. They include bleeding that cannot be controlled by endoscopic intervention, perforation, or clinical events that require abortion of the procedure. Delayed complications are complications that occur following the completion of the colonoscopy within 30 days of the procedure.
- *Complete and partial clip closure:* Degree of closure of the resection defect will be categorized as completely closed, partially closed, and not closed. Complete closure is defined if opposing resection margins are drawn together by clips from one side to the other, with gaps of less than 1cm between the clips. A site is considered partially clipped if only a portion of the defect could be closed¹⁷.
- *Factors associated with complications:* Factors that may be associated with complications, including polyp size, location of the polyp in the colon (right, left, rectum), histology, polyp morphology, time required for resection.

Endpoints of secondary analysis (entire study cohort):

- *Complete polyp resection:* Rate of complete study polyp resection a) at the initial colonoscopy and b) at first follow-up endoscopy
- *Polyp recurrence:* Rate of recurrent polyp at the resection site after complete polyp resection.

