3.2.10. Statistical analysis

3.2.10.1. Primary analysis: Comparison between clip group vs. no-clip group, 30 day follow-up)

Primary endpoint: Delayed bleeding complication.

We will assess the null hypothesis that clipping has no effect on delayed bleeding complications using a chi-square test to compare the two study arms (as randomized, intention-to-treat), or a Fisher's exact test if appropriate with a 5% significance level.

Secondary endpoint: Overall complications.

The secondary endpoint will be compared between the clip and no-clip arms using a chi-square test (or Fisher's exact test if appropriate) with a 5% significance level.

The primary endpoint (delayed bleeding complication) and secondary endpoint (overall complications) are planned to be used to support clip-labeling plans.

The main analyses of the primary and secondary endpoints will be done on a per subject basis. Additional analysis will be conducted at the unit per polyp. Clustering of polyps within patients (estimated to occur in approximately 5%) will be accounted for by using the method generalized estimating equations as well as mixed-effects-analysis with a random intercept for patient.

Subgroup Analyses: While the study is not powered to look at subgroups we will conduct exploratory analyses to determine if any difference in the clip and no-clip arms is modified by characteristics such as time of occurrence (immediate vs. delayed) and by etiology (bleeding, perforation, etc.). This examination will be descriptive because the study will unlikely be sufficiently powered for identifying differences as significant.

Explorative analysis of the effect of electrocautery setting: The comparison between the two electrocautery settings (low power coagulation vs. Endocut) will be explorative. Pilot data show that one third of participating endoscopists typically use low power coagulation and two thirds use Endocut. Acknowledging a possible effect of cautery on the incidence of complications there is a need to standardizing the cautery setting for the EMR procedure. Rather than using one cautery setting for all procedures, the cautery setting will be standardized by randomizing patients to one or the other setting. At the same time this randomization will allow an explorative analysis of the effect of cautery on complications. This

information, although descriptive, would provide valuable guidance to develop resection standards.

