3.2.10.3. Interim Analysis

An interim analysis will be conducted when we have enrolled 50% of the targeted 1020 patients, and completed 30-day follow-up on them. We will conduct an efficacy and futility analyses. For efficacy of clipping we will stop the trial if the two-sided p-value is less than 0.01. This alpha spending means that at the final analysis, a two-sided p-value less than 0.044 will be considered significant. At the interim look we will calculate the conditional power and terminate the study for futility if the conditional power is less than 20%. If the study will be continued, we will not modify the sample size based on the results of the interim analysis.

Because higher risk lesions may be more likely to benefit from clip closure the study should not continue to enroll patients if such benefit is apparent before study completion. We will therefore perform an interim safety sub-analysis for two groups of patients:

- (a) Patients with study polyps >4cm, and
- (b) Patients who are on anticoagulation or resume anticoagulation within 14 days of the polyp resection.

We assume that either group will contribute 10 to 20% to the study. We plan to conduct this safety analysis for each of these subgroups after 60 patients have been enrolled into either of the two subgroups (i.e. after enrollment of 60 patients with a >4cm study polyp and separately after enrollment of 60 patients who resumed anticoagulation after polyp resection). For example, the safety analysis would detect the occurrence of 2 vs. 9 delayed bleeding complications in the non-clip vs. the clip group as a significant difference (RR 4.5, 95% CI 1.01, 19.96). The study should cease to enroll these patients if the interim safety analysis shows a significantly increased relative risk in delayed bleeding complications in the non-clip group compared to the clip-group (see also Section on Monitoring).

A second safety analysis for these two groups will be part of the interim analysis after enrollment of 50% of patients (see above). Similarly, should this analysis show a significant difference in delayed bleeding complications, these patients should not be further enrolled.

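### The 20% allowance for defects that cannot be closed is handled like dropout, yet those patients stay in the intention-to-treat clip arm; if 3% is the rate in closed patients and the unclosed bleed at the no-clip rate, power is about 72%, not 80%.

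*Combined protocol and SAP*

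**What the plan says.** Section 3.2.10.4 takes an absolute difference of 5 percentage points, with 8% and 3% as the example, and continues: "Assuming a two-sided alpha of 0.05 and a power of 80%, the study will need to include a total of 730 subjects", or 365 per group. It assumes that in about 20% of patients clip "closure will not be considered possible. Therefore approximately 920 patients will need to be included". A further 10% for screen failures gives 1,020 consented. On losses after that point it says "we do not expect any dropouts".

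Four other sections bear on what happens to a clip-arm patient whose defect cannot be closed:

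- Section 3.2.2 (Inclusion and Exclusion criteria) has no criterion on whether the defect can be closed.
- Section 3.2.5 (Randomization process) randomizes "at the time of colonoscopy when a polyp has been identified as a study polyp" and adds: "Participants will therefore not be excluded because of non-compliance".
- Section 3.2.9.2 (Study endpoints) records closure as complete, partial or none: "A site is considered partially clipped if only a portion of the defect could be closed".
- Section 3.2.10.1 (Primary analysis) uses a "chi-square test to compare the two study arms (as randomized, intention-to-treat").

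Section 3.2.10.3 (Interim Analysis) sets the final threshold: "a two-sided p-value less than 0.044 will be considered significant".

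**The concern.** The sample size and the primary analysis assume different populations. Dividing by 0.8 keeps the planned power only if one patient in five drops out of the comparison, leaving about 730 who show the full 8% versus 3% contrast. Under intention to treat all 920 are compared, and the unclosed fifth of the clip arm pulls that arm's rate toward the no-clip rate. Extra patients partly offset a smaller difference, but a factor of 1/0.8 is not the right size for that purpose.

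The stated 80% is the yardstick for a null result, and section 3.2.10.1 says the endpoint is meant to support clip labelling. As written, a reader cannot tell whether the trial would miss the effect it was designed for about 8%, 20% or 28% of the time.

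**Working it through.** **Inputs.** From 3.2.10.4: 8% and 3%, two-sided alpha 0.05, power 80%, 20% not closable, 920 treated (460 per arm). From 3.2.10.1: chi-square test, as randomized. From 3.2.10.3: final threshold 0.044. The bleeding rate in unclosed patients, r, is not in the documents and is varied.

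**Step 1: reproduce the plan.** The two-proportion formula with pooled variance under the null is

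n = [z(0.975)·√(2p̄(1−p̄)) + z(0.80)·√(p₁(1−p₁) + p₂(1−p₂))]² / (p₁−p₂)²

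With p₁ = 0.08, p₂ = 0.03 and p̄ = 0.055, n = 325.2, or 326 per arm. The continuity correction, (n/4)·[1 + √(1 + 4/(n·0.05))]², gives 364.1, or 365 per arm and 730 in total. This matches the plan. Then 730/0.8 = 912.5, stated as about 920, and 920/0.9 ≈ 1,022, stated as 1,020.

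**Step 2: the intention-to-treat contrast.** If 3% is the rate in closed patients, the clip-arm rate is 0.8 × 3% + 0.2 × r. With r = 8% it is 2.4% + 1.6% = 4.0%.

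**Step 3: power with 460 per arm.** All pairs of binomial counts were enumerated, using the uncorrected chi-square test and 8% in the no-clip arm.

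| Unclosed patients (r) | Clip-arm rate | Power at 0.05 | Power at 0.044 |
|---|---|---|---|
| 8% (no benefit) | 4.00% | 73.4% | 71.6% |
| 6.75% (quarter of the benefit) | 3.75% | 79.4% | 77.9% |
| 5.5% (half) | 3.50% | 84.7% | 83.4% |
| 3% (full; also the case where 3% is the whole-arm rate) | 3.00% | 92.7% | 91.9% |

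At 0.044, power is 81.3% for a clip-arm rate of 3.6% and 79.0% for 3.7%, so 80% falls near 3.65%. That corresponds to r ≈ (3.66 − 2.4)/0.2 ≈ 6.3%, about a third of the benefit.

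**Step 4: unclosable lesions with a different baseline risk.** Hold the no-clip arm at 8% overall and keep the relative effect of 3/8 in closed patients, with no effect in unclosed ones. For a baseline b in unclosable lesions, the clip-arm rate is (3/8)(8% − 0.2b) + 0.2b.

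| Baseline in unclosable lesions (b) | Clip-arm rate | Power at 0.044 |
|---|---|---|
| 5% | 3.625% | 80.7% |
| 10% | 4.25% | 64.9% |
| 12% | 4.5% | 57.8% |

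**Step 5: checks.**

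- Crediting the interim efficacy look (0.01, then 0.044; simulated, no futility stop) gives 72.2% for 8% versus 4%.
- A continuity-corrected test gives 66.5% at 0.044 and Fisher's test 66.7%. With about 28 events expected per arm ((36.8 + 18.4)/2 = 27.6), small cells give no reason to use either.
- If unclosable defects were set aside before clip allocation, 0.8 × 460 = 368 per arm at 8% versus 3% gives 84.8% at 0.044.

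**The case against.** The strongest counter-reading is in section 3.2.5. It places the cautery allocation after inspection of the polyp and, in parallel, mentions clipping after resection. If clip allocation came after resection, unclosable defects could be set aside first; 730/0.8 would then be correct and power 84.8%. The reading is possible, but no section describes a feasibility check or removes anyone at that point. Section 3.2.6 goes straight from complete resection to closing or not closing as randomized.

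Four further points are fair in part:

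- The sentence on non-compliance follows a remark about adherence, and the one on dropouts rests on the short follow-up. Neither is about defects that cannot be closed. The argument stands without them, on the intention-to-treat test, the absence of an exclusion, and closure being recorded as a category.
- The 72% needs two assumptions: that 3% means closed patients, and that unclosed patients gain nothing. The plan does not say whether its 20% includes partial closures; if it does, zero benefit is severe. Hence the range.
- Setting 72% against 80% is not like for like, since the plan's 365 is continuity-corrected at 0.05 and the 72% is uncorrected at 0.044. A like-for-like comparison is less favourable: the continuity-corrected formula at 0.05 gives 67.6% for 8% versus 4% with 460 per arm.
- Section 3.2.6 allows clips in the no-clip group, which the figures here do not count. If, as an assumption, 5% of that arm bled at 3%, its rate would be 0.95 × 8% + 0.05 × 3% = 7.75%, and power against 4% would be about 67%.

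**Conclusion.** The concern holds. Under either intention-to-treat reading the 1/0.8 step is wrong as written. If 3% is the rate in closed patients, the step does not represent dilution; if 3% is the rate in the whole clip arm, the step has no stated reason.

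The size of the effect depends on the reading. Power is about 72% at the final threshold if 3% means closed patients and unclosed patients bleed at the no-clip rate, so the trial would miss that effect about 28% of the time. It recovers to 80% if unclosed patients keep about a third of the benefit. It is about 92% if 3% is the whole-arm rate. Confidence is high that the step and the analysis do not match. The 72% itself is conditional, because the documents give no bleeding rate for unclosed patients.

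**What to change.** Do not add patients. In section 3.2.10.4:

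1. State whether 3% refers to patients whose defect was closed or to everyone randomized to clipping.
2. State that patients whose defect cannot be closed stay in the clip arm for the primary analysis.
3. If 3% refers to closed patients, replace the division by 0.8 with the resulting intention-to-treat rates. Give the power at 460 per arm and 0.044 over a stated range of rates in unclosed patients, for example 8% (about 72%), 6.75% (about 78%) and 5.5% (about 83%). Say that these figures assume no clipping in the no-clip arm. Alternatively, report the intention-to-treat contrast detectable with 80% power, about 8% versus 3.65%.
4. If 3% refers to the whole clip arm, drop the 20% allowance as the reason for 920 and state power of about 92%.

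If unclosable defects are in fact meant to be set aside before clip allocation, sections 3.2.5 and 3.2.10.1 must say so.

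The cost is a few sentences, and a less favourable stated power if 3% refers to closed patients. There are no new patients or procedures, and the primary test is unchanged.

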3.2.11. Timetables

We expect to complete enrollment within two and a half years. The main outcome measure will be assessed between 30 and 45 days for each enrolled patient. The duration of the study to obtain information on the major outcome of interest is expected to be completed within three years.

- a) Length of participant involvement in the study: 5 years
- b) Estimated time to enroll enough participants to complete this study: 2.5 years
- c) Estimated time to achieve primary objective of the study: 3 years

3.3. Data and Safety Monitoring Plan

Appropriate consent documentation and clinical study documentation, progress of the trial, including assessments of data quality and timeliness, participant recruitment, and participant risk versus benefit will be monitored monthly by the principal investigator.

The DSMP includes the following:

- Use of standard procedures and precautions for colonoscopy with polyp resection.
- Post-procedure telephone follow-up call within 24 to 72 hours with an appropriate plan of action should any clinical signs suggesting complications occur.
- All patients will be asked to contact the endoscopist/or representative, their health care provider, or present to the local emergency room, should they experience any problems after the colonoscopy (i.e. abdominal pain, bleeding) (see methods section).
- Approximately 3-4 month call-back for follow-up colonoscopy.
- All serious adverse events will be reviewed by the principal and co-investigators to assess whether this complication was related to study participation following the event and by the DSMB. In addition, procedural complications will be reviewed at individual sites per local standard. These reviews will assure additional independent assessment and evaluation of possible adverse events.
 - For VA sites: All patients from the WRJ VA are subject to independent review for serious adverse events by the local complication board, which meets every three months. All serious adverse events that occurred during any endoscopy procedure are reviewed by the committee and graded according to the severity of the event.
 - For VA sites: The VHA information security officer will be solicited to review any potential security violations of the network protected study database.

3.3.1. Monitoring Plan

The main goals of monitoring the use of the clip as a nonsignificant risk device include

- 1) To secure compliance, and
- 2) To allow immediate evaluation of an unanticipated adverse device event (FDA, 21CFR 812.46)

The purpose of the monitoring plan is to outline the approach to monitoring this clinical trial. The plan is based upon verification of compliance with FDA regulations and guidelines and Good Clinical Practice (GCP) guidelines, which require monitor verification that:

- a) The rights and well-being of human subjects are protected
- b) The reported data are accurate, complete, and verifiable from source documents
- c) The conduct of the trial is in compliance with the currently approved protocol, with GCP, and with applicable regulatory requirements.

The monitoring focuses on the primary aim of the study and the safety of the Resolution Clip in its off label use as a non-significant risk as a non-significant risk device. Considering the safety profile of the clip and the potential that the clip will reduce complications, we plan off site monitoring where appropriate. This will include conference calls and upon request sending de-identified CRFs for review to the monitor according to the following time plan:

- The study will only commence at individual sites if all requirements as outlined in the monitoring plan are met.
- After 5 to 10 patients were enrolled at a site, the site will be monitored to assure adherence to the study protocol, especially with respect to eligibility, consent process, and completeness of data collection.
- Repeat monitoring will be conducted after 20 to 30 patients have been enrolled at a site.
- A final monitoring of each site will be performed after enrollment is complete.

On-site visits may be conducted based on individual performance criteria, especially with respect to adverse event reporting (e.g. sites with the highest or lowest reports of adverse events), and enrollment (i.e. sites that are far above or below target).

3.3.2. Data Safety Monitoring Board

- The DSMB consists of three independent gastroenterologists who are considered experts with respect to large polyp resection, and one statistician. After half of planned participating patients have been enrolled, the members of the DSMB will review all serious adverse events and review recruitment based on the proposed timeline.
- The study will be stopped should there be serious adverse events (bleeding, requiring additional interventions following the colonoscopy, perforation) related to study participation beyond what would be expected with respect to frequency or severity. The decision to stop the study will be made by the DSMB. The following stopping rules apply:
 - The study will be stopped should the interim analysis show a substantial difference between the clipping and non-clipping group of $p < 0.01$ (see Interim Analysis).
 - Patients with $>4\text{cm}$ polyps will no longer be enrolled should the interim safety subanalysis show a significant absolute difference in delayed bleeding complications between the clip and the non-clip group of at least 30% (see Interim Analysis).
 - Patients who are on anticoagulation or scheduled to resume anticoagulation within 14 days of a study polyp resection will no longer be enrolled should the interim safety subanalysis show a significant difference in delayed bleeding complications between the clip and the non-clip group (see Interim Analysis).

Research Materials. Data will be collected only if the subjects participate in the study. Data will be obtained only for research purposes.

Protection. Subjects will be afforded a variety of protections. First, all protocols will be IRB approved and subject to oversight by the local IRB. Second, once the data are collected they will be dealt with in an anonymous manner with adherence to HIPAA guidelines.

